As each patient completes 8 weeks of follow-up, all patient data will be sent to the Mayo Clinic, where an analyst will clean and curate the data made available through the Hugo platform. The analyst will then send the cleaned data for the YNHH patients to the Yale investigator team. The RA will then confirm the primary diagnoses in the YNHH Electronic Medical Record (EMR) for physician visits, emergency department visits, and inpatient admissions during the 8-week period by examining and comparing to the research database to determine if any encounters or diagnoses are missing in the research database.

The data points that we will validate in the Hugo Research Database from the YNHH Epic EMR will be:

- Encounter date
- Encounter type
- Primary diagnosis for encounter

We will also note if any additional physician visits, emergency department visits, and inpatient admissions are seen in either system (in the case of additional points in Hugo, we will also determine if they are from another health system). If any diagnoses are missing in the Hugo Research Database, we will determine from which visit that they were missing.

In addition, we will examine YNHH EMR data to determine what new medications were prescribed at discharge, and then we will examine pharmacy data to determine which of these prescriptions were filled by the patient.

Finally, at the end of the pilot study (i.e. at 8 weeks post-procedure), study participants will be called by the RA and asked to complete a close-out questionnaire (see Appendix) to determine their satisfaction with the process of answering queries and provide the opportunity for them to offer comments and suggestions for

improvement. They will also be asked at what health systems they received care over the past 8 weeks (including hospitalization, emergency department visit, repeat procedure), to assess if all pertinent data was captured in Hugo.

Close-Out Questionnaire, whereby study participants are called by RA at 8 weeks on a HIPAA-protected secure phone line and asked:

- 1. How was your overall experience using this technology (open-ended)?
- 2. How long did it take you, on average, to answer the questions that you were sent weekly?
- 3. How was the experience of answering questions (open-ended)?
- 4. Did you have any of the following in the past 8 weeks:
 - a. emergency department visit
 - b. admission to a hospital
 - c. re-operation
 - d. major complication

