Age, gender, date of birth and several categories of health information (provider encounters, notes, medication lists, problem lists, family history, allergies, laboratory findings, procedures, immunizations, vital signs, and medical record numbers) will be collected via the Hugo application. We will also be collecting data provided and synced to the Hugo application from the wearable devices including the Fitbit Charge 2 (heart rate ambulation and sleep), Nokia Body scale (weight), and the Kardia Mobile EKG (heart rhythm). In addition, we will obtain medication data from 2 major pharmacies.

The research associate will also access the patient's full medical record, with read-only access, within the YNHH Epic electronic medical record (EMR) system. This data will not leave the Epic EMR system in any way, and is only being used to verify certain categories of patient events to confirm that they have been included in the Hugo application. Data access to the YNHH Epic EMR will only be granted after all necessary trainings are complete and sign off is received from the Yale IRB and YNHH medical records department using the Yale New Haven Health System's Research Request for Medical Records Access form.

2.	How will the research data be collected, recorded and stored? After obtaining consent, patients will be requested to submit data from their Hugo personal health records to the study over SSL with a minimum of 128 bit encryption. This data will initially be transferred to Mayo Clinic to a data analyst associated with this project for cleaning. All YNHH patient data will then be shared using Signiant's Media Exchange Managed File Transfer (MFT). This platform is a web-based application used to share data packages over the internet through a secure channel. When being shared, the data will be encrypted using https secure protocol (Appendix). Access to this data will only by available to study personnel at Yale and Mayo Clinic, with collaborators at the Mayo Clinic receiving their own IRB approval.
3.	How will the digital data be stored? □CD □DVD □Flash Drive □Portable Hard Drive □Secured Server □Laptop Computer □Desktop Computer □Other
4.	What methods and procedures will be used to safeguard the confidentiality and security of the identifiable

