All data used at Yale will be provided by the Mayo Clinic over secure channels and encrypted during sending. Data will be stored on 3-lock compliant servers within Yale or on secure, Yale-issued IronKey devices. Only study personnel directly involved in data analysis with a need to access PHI will have access to these data. Any access to de-identified data will be completed via the Yale secure network or accessed via a secure connection to the Yale VPN. Please also see the Hugo Security Statement (Appendix). The sync for science platform is a personal

study data and the storage media indicated above during and after the subject's participation in the study?

health record that follows the Federal Trade Commission requirements for notification.

All portable devices must contain encryption software, per University Policy 5100. If there is a technical reason a device cannot be encrypted please submit an exception request to the Information Security, Policy and Compliance Office by clicking on url http://its.yale.edu/egrc or email [contact]

5. What will be done with the data when the research is completed? Are there plans to destroy the identifiable data? If yes, describe how, by whom and when identifiers will be destroyed. If no, describe how the data and/or identifiers will be secured.

Data will be maintained on secure, encrypted servers at Yale Center for Outcomes Research and Evaluation after completion of the research study for a minimum of 5 years after publication of our findings in a peer-reviewed journal (in such case as there is a need to return to the original data source to validate a finding or respond to a question).

After data is collected, deidentified data will be shared with collaborators, listed on the research protocol, from Johnson & Johnson. HIPAA identifiers will be removed prior to share and patients will be made aware via the consent process.

Study participants will always have access to their health data and the ability to download their personalized health record and take it with them. They will be given access to updates of the sync for science platform. After the completion of the study, we will also make summary level findings available to participants, without any identifiable personal health information.

6. If appropriate, has a Certificate of Confidentiality been obtained?

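### The Epic check runs on the file already cleaned at Mayo: valid for the curated database, but it cannot tell a Hugo gap from a cleaning effect

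*Protocol*

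**What the plan says.** Section I, item 4 (Research Plan) sets the route. When a patient completes 8 weeks, the data go to Mayo, "where an analyst will clean and curate the data made available through the Hugo platform". Next, "The analyst will then send the cleaned data for the YNHH patients to the Yale investigator team". The research associate then works from the Epic record "by examining and comparing to the research database to determine if any encounters or diagnoses are missing in the research database".

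The object of validation is named in the same section: "The data points that we will validate in the Hugo Research Database from the YNHH Epic EMR will be" encounter date, encounter type and primary diagnosis. The tracing rule for gaps is: "If any diagnoses are missing in the Hugo Research Database, we will determine from which visit that they were missing". Extra items found in Hugo are checked for whether they come from another health system.

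Section IV confirms the route. Item 2 says: "This data will initially be transferred to Mayo Clinic to a data analyst associated with this project for cleaning". Item 4 says: "All data used at Yale will be provided by the Mayo Clinic over secure channels and encrypted during sending".

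The purpose is worded differently in different places. Section I, item 1 makes obtaining electronic record data through the platform part of both aims. Item 4 says that the platform's own ability to merge four sources into research-ready form is being tested. Section IV, item 1 justifies access to Epic as a way to confirm that events reached the Hugo application.

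**The concern.** The file that is checked is not the platform's own output. It is that output after a person has cleaned and curated it. Two different questions can be asked of the comparison:

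- Does the curated research database hold the encounters that Epic holds?
- Did Hugo deliver them?

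The plan answers the first. Its aims and its stated reason for opening Epic concern the second. If an Epic encounter is absent from the cleaned file, it may never have reached Hugo, or it may have been removed or merged in cleaning. If a date, type or diagnosis disagrees, Hugo may have delivered it wrongly or cleaning may have recoded it. If an item matches, Hugo may have delivered it in usable form or cleaning may have made it usable. Tracing a gap to a visit settles none of these.

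At stake is what the pilot can report. A feasibility study should tell the sponsor which step failed, because a portal or platform gap and a data-handling gap call for different remedies.

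**Working it through.** **Figures in the protocol.** No capture rate, cleaning rate, threshold or power figure is stated for this check, and metric groups A to C in the Research Plan list no capture rate. There is no figure to reproduce. Section I, item 13 treats the study as a feasibility pilot without a clinical primary outcome. The check covers the 30 YNHH patients (Section I, item 6: 15 bariatric + 15 ablation = 30).

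**Step 1: can the check run before cleaning?** Section I, item 4 orders the steps as Hugo, Mayo cleaning, Yale, comparison. Section IV, item 2 gives the same order, and Section IV, item 4 makes Mayo the source of all data used at Yale. As written, the encounter-level comparison runs only on post-cleaning data.

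**Step 2: does the tracing rule separate the steps?** It names the visit for a missing diagnosis and the health system for an extra item. Neither identifies the portal, Hugo or cleaning as the place of loss.

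**Step 3: how could the result be affected?** Three assumed quantities are needed, none of them in the protocol:

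- c = share of Epic encounters that are present and usable in the Hugo export
- l = share of those that are lost in cleaning
- r = share of the remainder that cleaning makes usable

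Observed capture = c(1 − l) + (1 − c)r, and the error relative to the platform is (1 − c)r − cl.

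With c = 0.90:

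| l | r | Observed capture | Error (points) |
|---|---|---|---|
| 0 | 0 | 0.90 | 0 |
| 0.02 | 0 | 0.90 × 0.98 = 0.882 | −1.8 |
| 0.05 | 0 | 0.90 × 0.95 = 0.855 | −4.5 |
| 0.10 | 0 | 0.90 × 0.90 = 0.810 | −9.0 |
| 0 | 0.25 | 0.90 + 0.10 × 0.25 = 0.925 | +2.5 |
| 0 | 0.50 | 0.90 + 0.10 × 0.50 = 0.950 | +5.0 |
| 0.05 | 0.50 | 0.855 + 0.050 = 0.905 | +0.5 |

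Over the grid c = 0.80 to 0.95, l = 0 to 0.10 and r = 0 to 0.50, the extremes are:

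- c = 0.95, l = 0.10, r = 0: 0.855 − 0.95 = −9.5 points
- c = 0.80, l = 0, r = 0.50: 0.90 − 0.80 = +10.0 points

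The last row of the table shows that loss and repair can nearly cancel, so a plausible total does not show that cleaning was neutral.

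**Step 4: how far can repair go?** The protocol describes no Epic access for the Mayo analyst. Repair can therefore apply only to records that Hugo delivered in unusable form, not to encounters it never delivered. If the whole shortfall is undelivered encounters, r = 0 and any error is downward or nil.

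**The case against.** The strongest reply is that the check fits the object it names. The Research Plan validates the Hugo Research Database. For surveillance, whether the delivered database holds the encounter is a proper question, and comparing that database with Epic answers it. This stands: for the end product the comparison is valid. The difficulty arises only when the result is read as platform performance, which the aims, the stated test of the platform and Section IV, item 1 all invite.

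A second reply points to other safeguards. Section I, item 2 speaks of cleaning, reviewing and verifying data on a rolling basis. The Research Plan has the platform itself checked at the 2-month call for each health system the patient names. Section IV, item 5 keeps data for at least 5 years in case the source must be revisited. These help, but the first describes no check before cleaning, the second works at health-system level rather than by encounter, and the third does not promise a pre-cleaning export.

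A third reply is that cleaning rules and logs usually sit in a data management or analysis plan. That is fair, and their absence here is not the point. The point is the order of steps and the tracing rule, which this protocol does fix.

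A reader might go further and infer that platform capture is misstated, or that cleaning flatters Hugo. The protocol does not support this. It nowhere says that cleaning drops, recodes or repairs encounters; a loss in cleaning would count against Hugo, not for it; and no stated capture figure exists to be wrong.

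**Conclusion.** The concern holds in a limited form. The Epic comparison validates the curated research database. It cannot by itself show what reached Hugo or how the platform performed, because every discrepancy mixes platform and cleaning effects and the plan traces gaps only to a visit.

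The size is unknown. The error may be downward, upward or zero, and the range of −9.5 to +10.0 points rests wholly on assumed values. The conclusion assumes that the steps run in the order written and that no pre-cleaning comparison is specified elsewhere. This is a cheap improvement in what the pilot can attribute, not a demonstrated error in a result.

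**What to change.** Amend the data transfer and validation text in Section I, item 4:

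1. Keep the Hugo export for each of the 30 YNHH patients as it stood at transfer to Mayo, with a log of records removed, merged, recoded or repaired.
2. Look up in that export each Epic encounter, date, type or primary diagnosis that is not matched in the cleaned file. Class it as *never in Hugo* or *in Hugo, lost or altered in cleaning*.
3. Use the log to find matched items that cleaning altered. The lookup of unmatched items cannot reveal these.
4. Report capture twice against the same set of Epic encounters: once for the platform export and once for the curated database. Align Section IV, item 1 with whichever object each figure describes.

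If the exports were not kept, describe the result as applying to the curated database only.

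The cost is storage of the exports, upkeep of the log and a small lookup confined to discordant items. No change to enrolment, patient contact or the Epic review is needed.

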Because the mobile health platform (Hugo) obtains patient data through patient portals, all patients who connect will need a YNHH MyChart account. The RA will assist the patients in creating a MyChart account. On a desktop computer, the RA will log into her YNHH Epic Hyperspace account. She will look up the given patient and then enable the patient to obtain a MyChart account through the "Launch MyChart Signup" functionality. The patient will then confidentially create a MyChart account (the RA's YNHH Epic Hyperspace account is automatically locked) by entering his/her own username, password, and retyping the password. Once the patient has completed the MyChart sign-up process, then the RA will assist the patient in creating and activating an account for the mobile health platform, Hugo, on the patient's personal smartphone. Some patients may need to reset their MyChart password, and the RA will enable them to do so. Some patients may have forgotten their MyChart username, and the RA will be able to provide this information to them through the "Launch MyChart Signup" functionality. The RA will also assist the patient in connecting their mobile health platform account with other health systems where they have received care by showing the study participant how to enter their patient portal credentials, provided that these health systems are connected to the mobile application, as well as to pharmacy portals where they have received medications (if that includes CVS or Walgreens). Patients will also receive a syncable device relevant to their procedure (i.e. AliveCor Kardia Mobile for catheter ablation of atrial fibrillation or Nokia Body digital weight scale for bariatric surgery patients and Fitbit for all patients). At this time, patients will also complete their pre-operative/baseline questionnaires so that the RA is present to assist them. The RA will also ask patients to obtain and upload their continuity of care document (CCD) if they receive care in a health system that is not connected to Hugo, at both enrollment and again at 8 weeks; the RA will also ask patients to obtain credentials, if necessary, and connect portals to health systems where they receive care that are connected to Hugo but were unable to connect at enrollment. Patients will also receive a follow-up email from the RA that includes user guides for the devices they have received (Appendix).

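### For primary diagnosis, the Epic reference is read with the Hugo-derived data already in hand; listing the Epic encounters first would be a cheap safeguard

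*Protocol*

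**What the plan says.** All of this stands in the Protocol, Section I, item 4 (Research Plan), unless noted.

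- **Order of work.** After a patient's eight weeks, the data go to the Mayo Clinic for cleaning and curation. "The analyst will then send the cleaned data for the YNHH patients to the Yale investigator team". The next step is: "The RA will then confirm the primary diagnoses in the YNHH Electronic Medical Record (EMR) for physician visits, emergency department visits, and inpatient admissions". This is done by "examining and comparing to the research database to determine if any encounters or diagnoses are missing in the research database".
- **Fields.** "The data points that we will validate in the Hugo Research Database from the YNHH Epic EMR will be" three: encounter date, encounter type, and "Primary diagnosis for encounter".
- **Both directions.** "We will also note if any additional physician visits, emergency department visits, and inpatient admissions are seen in either system", and extra Hugo entries are checked for origin in another health system. "If any diagnoses are missing in the Hugo Research Database, we will determine from which visit that they were missing".
- **Other checks on completeness.** At about two months the RA telephones patients to learn where they sought care, and Hugo is checked for data from those systems. The close-out questionnaire asks about emergency visits, admissions, re-operations and complications, and the reasons for visits, admissions or re-operations.
- **Handling of Epic data.** Section IV, item 1 (Confidentiality and Security of Data) gives the RA read-only access, states that these data stay inside Epic, and limits their use to verifying that events are included in Hugo.

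The text does not say that Epic is read before the Hugo data are seen, and it mentions no second reader.

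**The concern.** Epic is the standard against which the Hugo Research Database is judged. A reference is most useful when it is recorded without knowledge of the result under test. Here the RA already has the Hugo-derived data, reads the chart by comparing it with them, and has a task framed as confirming.

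This matters only where the reading involves judgement. A visit may carry several diagnoses, and someone has to decide which is primary. Two entries may word one condition differently, or one may give a symptom where the other gives a disease. With the Hugo entry in view, the easy decision is the one that agrees with it.

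Obtaining electronic record data is a named feasibility element of both specific aims. The Epic comparison is the only check of Hugo's diagnoses against a medical record that the protocol describes. The end-of-study chart abstraction has a different purpose, to understand the procedures better, and is not described as a comparison with Hugo. A diagnosis result that leaned towards Hugo would therefore not be corrected elsewhere.

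**Working it through.** **1. No figure to reproduce.** The protocol gives no agreement rate, target or statistic. Section I, item 13 marks statistical considerations as not applicable, because this is a feasibility pilot without a clinical primary outcome.

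**2. Order of work.** The cleaned data are sent to Yale, and the RA *then* turns to Epic. The comparison is how the chart is read, not a later step. So the protocol itself fixes that the reference is read with the Hugo value available.

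**3. Which outputs are exposed.**

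| Output | Room for judgement |
|---|---|
| Encounter date | Little |
| Encounter type | Little |
| Encounter present or missing | Little; finding gaps needs both sources |
| Primary diagnosis | Some: which one is primary, and whether two wordings match |

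**4. Illustration of size (all rates assumed).** Let A be the true agreement on primary diagnosis, g the share of true disagreements accepted as matches, and h the share of true matches scored as mismatches. Then

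observed agreement = A(1 − h) + (1 − A)g.

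*Knowledge of the Hugo value favours a match (g from 0 to 0.5, h = 0):*
- A = 80%: 0.80 + 0.20 × 0.5 = 0.90, so 80% to 90%.
- A = 90%: 0.90 + 0.10 × 0.5 = 0.95, so 90% to 95%.
- A = 95%: 0.95 + 0.05 × 0.5 = 0.975, so 95% to 97.5%.

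*Matching too strict (g = 0, h = 0.05):*
- A = 90%: 0.90 × 0.95 = 0.855, or 85.5%.

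*Both errors (g = 0.25, h = 0.05):*
- A = 90%: 0.855 + 0.025 = 0.88, or 88%.
- A = 80%: 0.76 + 0.05 = 0.81, or 81%.

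Errors that only favour a match raise agreement. Loose or strict matching can move it either way.

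**5. Against sampling error.** Section I, item 6 plans 30 Yale patients. For 30 independent units at 90%, the 95% half-width is 1.96 × √(0.9 × 0.1 / 30) = 0.107, or 10.7 points. That is wider than most of the shifts above. It does not excuse them, since a confidence interval does not cover bias, but it puts their size in proportion.

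**The case against.** The case against has several parts, and much of it stands.

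- **The task is mainly a search for omissions.** This is right. The stated purpose is to find what is missing from the research database, and that needs both sources. It does not need them at the same moment: an Epic list made first finds the same omissions.
- **Hugo is not an independent coding of the visit.** Hugo obtains its data through patient portals, so for Yale encounters it draws on Yale's own record. The documents do not say how often the two diagnosis entries would differ. The difference could be small.
- **Matching rules may sit in an analysis plan or data manual that is not shown.** This is accepted, and the lack of a rule is not held against the protocol. The order of work is different. The protocol fixes it, and a later document cannot undo it once charts have been read beside the Hugo data.
- **The two-way comparison is already planned.** It is, and it should be kept.

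Three stronger readings are tempting but unsupported.

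1. *Agreement is likely overstated.* No agreement measure is defined, and without a known matching rule the error could run either way.
2. *This is the pilot's only test of correctness and completeness.* The two-month call and the close-out questionnaire also test completeness, although from patient recall.
3. *The RA is checking their own work.* The protocol does say "The RA will also assist the patient in connecting their mobile health platform account with other health systems", but the Epic check concerns Yale encounters. A Mayo analyst, not the RA, cleans the data, and nothing shows that the RA has a stake in the result.

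Nor can a size be claimed by assuming that some share of encounters, say 5% to 20%, carry non-identical diagnoses. The resulting shift of 5 to 20 points merely restates the assumption, and it needs every such case to be called the same way. If half were accepted as matches, it would be 2.5 to 10 points.

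**Conclusion.** The point holds in a limited form. The protocol has the Epic reference read after, and by comparison with, the Hugo-derived database, under a task worded as confirming. For primary diagnosis, the one validated field open to judgement, this may favour a match. Date, type and missing encounters are little affected.

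Neither the direction nor the size of any net error can be derived from the documents. The figures in the working show only what assumed error rates would do. The conclusion rests on two assumptions: that some Yale encounters carry diagnosis entries that are not plainly identical in the two sources, and that no unseen document already requires Epic to be read first.

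This is a minor point and a cheap improvement, limited mainly to primary diagnosis. It does not threaten the pilot's aims.

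**What to change.** Keep the same RA and the same charts, and change the order.

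1. For each Yale patient, the RA lists from Epic all physician, emergency department and inpatient encounters in the eight-week window, with date, type and primary diagnosis as written. This is done without opening the Hugo file, and the list is then closed.
2. The RA then opens the Hugo file and makes the two-way comparison already planned.
3. Pair encounters **without** requiring date and type to be identical. Both are fields under validation. If they served as the matching key, an error in either would appear as one missing plus one extra encounter instead of as a date or type error.
4. Report diagnosis match at two levels: identical code or term, and same condition.
5. Hold the Epic list in a way that respects the statement in Section IV, item 1, that these data stay within Epic. Otherwise reconcile that sentence with the comparison and the end-of-study abstraction in Section I, item 4.

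**Cost.** Slightly more recording per encounter, a short addition to the Research Plan, and the reconciliation in step 5. No second reader is needed. Reported agreement may come out a little lower.
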